5.9.2 Storage

Storage of study drug will be maintained by the NYU-Investigational pharmacy, Study drug can be stored at room temperature. The investigational Pharmacy has 24/7 temperature logs.

5.9.3 Dispensing of Study Drug

The NYU Investigational Pharmacy will dispense study drug. Study team personnel will check drug reconcillation at each study visit.

5.9.4 Return or Destruction of Study Drug

At the completion of the study, there will be a final reconciliation of drug shipped, drug consumed, and drug remaining. This reconciliation will be logged on the drug reconciliation form, signed and dated. Any discrepancies noted will be investigated, resolved, and documented prior to return or destruction of unused study drug. Drug destroyed on site will be documented in the study files.

6 Study Procedures

Table 1 provides a complete list of the procedures at each study visit (in the office or via telemedicine 2-way conferencing) and figure 7 provides a timeline for the procedures at visits.

Table 1: Study procedures

Table 1. Study procedures	\/:a:4.4	Violt 0	Visit 3	Visit 4
	Visit 1	Visit 2	VISIT 3	VISIT 4
Procedure	Baseline/R	Crossover 1	Crossover 2	Final
Consent/ascent	Ø			
Urine pregnancy test (reproductive females)	Ø			Ø
Inclusion/exclusion criteria	Ø			
Concomitant medications/compliance check	Ø	Ø	Ø	Ø
Vital signs (temperature, weight)	✓	₫	✓	Ø
Metabolic panel	Ø	Ø	\square	Ø
Urinalysis	v	\square	\square	V
CBC	V	\square	V	\square
12-lead ECG*	V	\square	V	Ø
Physical/neurological examination	v	\square	\square	V
Adverse event questioning	V	\square	V	\square
OH-Questionnaire	Ø	\square	Ø	☑
24-h ambulatory BP recording	Ø	\square	\square	☑
24-h urine catecholamine excretion	V		V	Ø
Supine/seated/standing BP	V		V	Ø
Beat-to-beat BP or HR at rest	V		V	Ø
Beat-to-beat BP during Stroop (Office)	V		V	Ø
HR with serial 7s subtractions (Virtual Visit)	✓	✓	Ø	Ø
Symptom/AE diary collection		\square		\square
Dose de-escalation		Ø	\square	Ø
Washout		Ø	Ø	
Dose adjustment day safety phone call		Ø	Ø	
Day 7 adverse event monitoring phone call	Ø	Ø	Ø	☑

CBC; complete blood count, ECG; electrocardiogram, BP; blood pressure, AE, adverse event; R; randomization.

Visit 1. Baseline/Randomization:

Patients will be screened for eligibility and enrolled in the trial. Informed consent or ascent will be obtained. Patients will be given a tutorial and provided with written instructions on using the ambulatory blood pressure monitors and 24-h recordings will be obtained. Supine/sitting/standing office blood pressures will be measured. RR-interval and beat-to-beat blood pressure will be recorded for 5 minutes before and during a Stroop test (3-minutes) and during serial 7 subtractions (3 minutes). Patients will be asked to rate their symptoms of orthostatic hypotension on the validated orthostatic hypotension-questionnaire (OH-Q)⁴². Baseline safety bloods (CBC & metabolic panel), a 12-lead ECG and a physical and neurological exam will be obtained. After completing all baseline measures, patients will be randomized to the treatment order sequence (Fig. 6) in a 1:1:1 ratio. For patients that opt to continue follow-up via 2-way telemedicine conferencing, investigators will ensure that the patient has access to a validated blood pressure and heart rate monitor, weighing scale and thermometer at home. These will be provided, if needed. Patients will be given a continuous, automatic, wireless wrist-based heart rate tracker (Fitbit Charge HR, Fitbit, USA), which will be synchronized to allow remote monitoring at the Center. Patients and caregivers will be trained in how to perform a timed active stand test and to obtain blood pressure and heart rate supine (5-min), seated (2-min) and standing (5 min). Written instructions and a video guide will be provided.

Before leaving the office, patients will be instructed to keep a daily symptom diary (a modified version of the Rhodes Nausea/Retching/Vomiting Index³⁹ with additional space to note adverse events). Additionally, patients will be told to contact the Center to report any adverse event. They will be contacted by phone call on the day that they adjust their dose. Seven-days into their treatment arm patients will be contacted again to monitor tolerability and adverse events. Thereafter, we will contact patients on a weekly basis to monitor potential adverse events. They will return for the next study visit in 28-days.

Patients that have been seen at the Center within the last 3-months may have the option of completing the study screening and enrollment proceedures via virtual visits, at the discretion of the PI (a treating investigator).

Visit 2. Crossover #1:

For in office visits, patients will be instructed to take their study pill 3-h before attending the office visit. The timing of the medication and testing will be noted in the case report forms. Patients will bring with them to the office visit a 24-hour urine collection for urine catecholamine assay. They will be instructed to arrive wearing the ambulatory BP monitor. Upon arrival at the clinic, vital signs will be taken and blood pressure will be measured supine, seated and standing. Ambulatory monitor blood pressure values will be calibrated against simultaneous measurements of blood pressure in the opposite arm using an automated sphygmomanometer during the orthostatic challenge. Ambulatory recordings will be downloaded and the data reviewed for quality. If recordings are found to be inadequate, they will be repeated with the patient remaining on the same dose of medication for 1 additional day before titrating down and washout. Patients will be instructed to return their unused medications to monitor compliance Beat-to-beat BP and RR interval changes before/during stoop and serial 7 subtractions will be repeated. Patients will have blood drawn and urine collected for safety measures and a 12-lead ECG will be performed. Neurological and physical exam will be performed. Patients will be dispensed and dosing instructions will be provided (Appendix).

[figure not shown]

Fig 8: Details of the telemedine visits: Study visits may be performed virtually, through 2-way audio visual conferencing. See text for details.

As shown in Figure 8, for telemedicine visits, prior to the visit, investigators will ensure patients have access to 2-way video conferencing with audio and that continuous HR measurements can be acquired from the wireless wrist tracker. Symptoms diaries will be collected. Patients will be instructed to continue their three times daily dosage of carbidopa. Safety labs, ambulatory blood pressure monitoring and 24-h urine collections will be performed while at the steady state.

Before the call, patients will be instructed to (1) weigh themselves in the morning, (2) to take their study medication 3-h before the scheduled time of the teleconference, (3) email a photograph of their unused pills for medication compliance check, (4) be wearing their ambulatory monitor at the time of the video call, and (5) have their wrist-based heart rate tracker on.

When video conferencing begins, to monitor vital signs, patients will be instructed to take a blood pressure and heart rate reading (while seated), obtain their temperature, and display the results on screen. On the opposite arm, a simultaneous manual measurement on the ambulatory monitor will be performed, and both measurements noted in the case report forms for calibration of the ambulatory readings. Patients will be guided through a timed active stand test and acquire blood pressure and heart rate measurements supine, sitting and standing. After recovering, continuous HR will be obtained from the wireless wrist tracker for 5 minutes at rest while seated and over a 3-minute period while the patient is performing serial 7 subtractions, as described.⁵

The following is a summary of how a physical and neurological evaluation will be performed during a telemedicine visit:

ASE II STUDY Page 16

All aspects of the physical and the currently performed neurologic exam can be performed via telemedicine except auscultation (which can be assessed in other ways). The following is an outline of how this will be performed with video monitoring:

- Vital signs including height, weight, temperature (the patient is asked to have a home thermometer available), and blood pressure and heart rate via the 24 hour ambulatory monitor.
- General appearance: The general appearance can be evaluated with video monitoring and conversing and watching the patient throughout the telemedicine visit.
- HEENT: The patient can perform ocular movements, the sclera can be evaluated, and the clinician can evaluate the eyes and throat via the video screen and a flashlight can be utilized when needed for additional visualization.
- CV: Heart rate and blood pressure can be evaluated as previously mentioned.
- Pulm: We can have the patient cough and deep breath to evaluate for presence of new cough, chest congestion, and wheezing. FD patients are familiar with performing these types of evaluations by phone as they are often calling from around the world with questions or concerns about their respiratory status.
- Abdomen: The abdomen can be evaluated visually including the integrity of the gastrostomy tube and looking for distention.
- GU: Information can be obtained via the review of systems and the safety urinalysis with microscopy.
- Lymphatics: Usually only evaluated if there is a problem or concern.
- Musculoskeletal: Upper extremity and lower extremity musculature can be visually evaluated, along with change in weight.

Skin: The skin be evaluated visually during the televisit.

- Neuro: Cognition, gait, facial expression, coordination, and evaluation for tremor can all easily be evaluated during a televisit.
- A full review of systems can be performed during the televisit and if there are any questions or concerns related to an organ system then subsequent follow up can occur either at the NYU Dysautonomia Center or by visiting a local physician who we can communicate with after his/her evaluation.

This protocol will be repeated for each telemedicine visit.

Before cross over onto the next allocated treatment and beginning their new batch of medications, patients will be titrated down (reducing the dose to 2/3 and then 1/3) and washed out for 2-days. Seven-days after being on their treatment, they will be contacted again. Thereafter, we will contact patients on a weekly basis to monitor potential adverse events. Patients will undergo another visit (virtual or in-office) after 28-days of treatment bringing with them a 24-hour ambulatory recording, a 24-h urine collection. They will be instructed to continue documenting their symptom in the custom diary.

Visit/Televisit 3. Crossover #2:

At this visit, supine/seated/standing BP and beat-to-beat changes during stoop will be measured 3-h post dose or heart rate during serial sevens testing. Ambulatory recordings will be calibrated against office blood pressure readings for in-office visits and will be downloaded and reviewed for data quality. Safety bloods and 12-lead ECG will be obtained and physical examination will be conducted. Patients will be questioned about adverse events and score the OH-Q. They will be crossed over to receive their final treatment allocation, depending on their randomization sequence. Dosing instructions will be provided to titrate down for 2-days and washout for 2-days. Patients will be asked to maintain their symptom diary and return for follow-up in 4-weeks with a 24-hour urine collection and ambulatory BP recording and the symptom diary. As described for visit 2, patients will be contacted on the day that they begin their new treatment and seven days after being on their treatment. Thereafter, we will contact patients on a weekly basis to monitor potential adverse events. Patients will return for follow-up after 28-days of treatment bringing with them a 24-hour ambulatory recording and a 24-h urine collection. These visits may be performed virtually, with the standard operating proceedures outlined in Figure 8. They will be instructed to continue documenting their symptom in the custom diary.

Visit/Televisit 4. Final:

At the final study visit or televisit (see Fig 8 for details), 3h post-dose we will conduct the orthostatic blood pressure measurements supine/seated/standing while obtaining concomitant measurements of blood pressure of the ambulatory monitor or using the ambulatory monitor for televisit patients. Vital signs and Stroop-induced changes in BP will be assessed in office or heart rate monitoring via the iPhone application while performing

serial sevens will be done during the televisit. We will obtain safety bloods, urinalysis, a 12-lead ECG and all patients will undergo a physical and neurological evaluation. Patients will fill the OH-questionnaire and be questioned about adverse events. Ambulatory recordings will be downloaded to check for data quality and 24-h urine collections will be assayed for catecholamines. Diaries and unused medications will be collected or returned to the Center. Dose de-escalation instructions will be provided for the end of the study.

Follow-up phone call:

One week after completion of the cross over periods, patients will receive another follow-up phone call to monitor any adverse events.

24-hour Ambulatory Blood Pressure Monitoring:

Patients with FD frequently undergo ambulatory BP monitoring while keeping a detailed log of their activities (sleep/meal-times/medications/posture/symptoms). Compliance is excellent and they tolerate the procedure well. The majority of patients have home nursing support that will aid with fitting the ambulatory monitors at home, and we will also provide a tutorial as well as written instructions on how to fit the monitor (Appendix), including instrumentation on the non-dominant arm and the distance (in cm) from the elbow. We will use video calls to aid fitting the ambulatory monitor when necessary.

To ensure consistency between measurements, cuff size will be recorded in the case report forms and the same cuff size will be used throughout. We will standardize the times of the recordings so that the data collection begins and ends at the same time (i.e., is over the same 24-h period; e.g., 9 AM to 9 AM) on each treatment period. Monitors will be calibrated prior to use following the manufacturers guidelines (SpaceLabs, Service Manual). For this study, patients will be fitted with a validated ambulatory blood pressure monitor (90207 monitor, SpaceLabs, Washington, USA) and instructed to go about their daily activities. For in office visits the patients will be instructed to arrive for the appointment still wearing the ambulatory monitor and simultaneous measurements of blood pressure will be obtained with an automated sphygmomanometer during the orthostatic challenge test to recheck the calibration (Colin Pilot, Texas, USA). For televisits the patients will be instructed to keep the ambulatory blood pressure monitor on during the televisit so that blood pressures and heart rates may be obtained under video supervision by the clinician. Recordings will be downloaded at study visits and repeated if the success rate is not adequate (<80%) or office and ambulatory readings differ by more than 20%. Due to afferent baroreceptor dysfunction, the episodes of paroxysmal hypertension in FD occur predictably in response to emotional or cognitive stimuli. Thus, it is the blood pressure instability during the day (when the patient is awake) that is the major contributor to the increased overall variability. 25 Therefore, our primary efficacy endpoint will focus on the change in blood pressure variability during waking hours (determined from the patient's activity log). Since nocturnal BP fall contributes significantly to 24-h variability, and a non-dipping pattern is associated with end-organ target damage, 43 we will look at changes in blood pressure variability during the entire 24-h period independently. We will also evaluate the weighted variability, to look at the influences episodes of paroxysmal hypertension during the nighttime sub-period. Variability in systolic, diastolic and mean blood pressures will be examined independently.

The following variables will be evaluated and each may have different primary determinants.²⁵

Average blood pressures: The theoretical underlying level of blood pressure calculated by averaging several blood pressure values collected over the defined time periods (entire recording, sleep hours, wake hours).

Standard Deviation: The variability in blood pressure overtime determined by the standard deviation (entire recording sleep hours, wake hours).

Coefficient of Variation: The measurement of blood pressure variability based on the standard deviation that also takes into account the underlying level of BP. Calculated as follows: CV = [SD/mean BP] x 100.

Nighttime Dipping: Analysis of the circadian pattern based on the difference in average daytime and nighttime values and expressed as a percentage. With normal night-time "dipping" defined as a 10% fall in BP during sleeping hours.⁴³

Weighted Standard Deviation: Using a "weighted" measurement of standard deviation of 24-h ambulatory BP that avoids the contribution of nocturnal dipping to the overall variability, but still includes the BP variability during the night has been suggested as an accurate measurement of cardiovascular risk.²³ Calculated as follows: wSD = [daytime SD x14 + nighttime SD x6]/20).

Morning Surge in Blood Pressure: The increase in blood pressure that occurs on awakening from sleep and is exaggerated in patients with FD. The morning surge will be calculated as the difference between the mean

Version: 5.0 (date Echruany 12, 2019)

Version: 5.0 (date February 12, 2018)

systolic blood pressure during the hour that included the lowest blood pressure during sleep and maximum value detected within 2-h of awakening from sleep (as previously described¹⁰)

Page 18

Abbreviations: BP, blood pressure; SD, standard deviation; CV, coefficient of variation. wSD, weighted standard deviation.

Questionnaires:

Patients will complete 2-questionnaires to assess tolerability.

OH-Q: The orthostatic hypotension questionnaire (abbreviated to OH-Q) was recently validated and consists of 10-items graded on an 11-point scale (0 to 10).⁴² Six items assess symptoms of neurogenic OH and 4 address the impact they have on activities of daily living (Appendix 1).

Symptom Diary: As we did in our previous trial, ¹³ we will use a tailored questionnaire to examine symptoms over the treatment period and the used of as needed medications. Each day will have a designated page. Since nausea/vomiting and hypertension occur together in FD we will use a diary consisting of a simplified version of the Rhodes Index ⁴⁴ symptoms of nausea/retching, with items addressing vomiting/throwing up omitted, as most participants will have had anti-reflux surgery to prevent vomiting (fundoplication), graded on a 5-point scale (appendix 2). The diary will also include space to write down any adverse events on a daily basis.

Catecholamines:

Prior to arriving for a study visit or performing a televisit, patients will be asked to collect a 24-hour urine sample in a bottle shielded from light containing preservative. Patients will be instructed to refrigerate their sample and bring it on the morning of their visit in a cool bag or provided with a prescription to take it to a local laboratory. Catecholamines will be measured using high-pressure liquid chromatography as previously described. 45 Because urine catecholamine collections reflect periods of sympathetic nerve activation over an entire day, in this particular circumstance urinary excretion will more clinically useful information, than a plasma "snap-shot" obtained from a blood draw at the office, which has the emotional component of a having and IV inserted in the arm (which despite not feeling pain, is not well tolerated by these patients).

Autonomic Testing:

The effect of carbidopa on blood pressure will also be investigated 3-h post dose. All procedures will be carried in a temperature-controlled environment by investigators trained in performing autonomic function tests and experience in working with FD patients. Blood pressure will be measured using finger plethysmography (Finometer/PortaPres) and the arm supported at heart-level on a custom made rest for the in-office patients. RR intervals will be recorded from chest wall electrodes. All data will be synchronized, digitized and acquired using the PowerLab System (AD Instruments). Recordings will be made for 5-minutes while the patient is relaxed, calm and breathing spontaneously (pacing the breathing it impossible for most patients with FD to achieve). Baseline variability will be assessed using descriptive statistics (SD, CV see above for calculations). Blood pressure responses to cognitive stress will be evaluated during the Stroop Word Color Test Application administered on an iPad (First Generation, Apple Inc.) over 3 minutes as described. The maximum increase in blood pressure while concentrating on the Stroop will be used to define cognitive-stress induced hypertension. We have successfully obtained autonomic data using these techniques before. For the patients performing televisits the heart rate and unrestrained sympathetic activity will be measured using a smart phone application under visual supervision by the clinician.

7 Statistical Plan

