8.6.1 Data Monitoring Committee

Safety data will be collected at each study visit (12 lead ECG, urinalysis, CBC, metabolic panel, vitals, neurological & physical examinations). In addition, to further monitor safety between study visits, we will contact

by phone patients on the day of and again 7-days after adjusting doses to question them about potential adverse events. We will continue to call patients on a weekly basis during the outpatient phase to monitor adverse events (table 2). All data will be collected on standardized case report forms. Data will be entered into a study database created on the REDCap platform and hosted by NYU's Clinical and Translational Science Institute (CTSI). All data will be de-identified, encrypted and stored behind a secure firewall accessible only to designated investigators. To check for potential data entry errors, data will be graphed and examined for outlying values prior to analysis.

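### If the blanks in Table 1 are genuine, periods 2 and 3 start nominally 32 and 64 days after the last pregnancy test; repeating it at Visits 2 and 3 is a cheap safeguard

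*Combined protocol and SAP*

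**What the plan says.** Section 6 introduces the schedule with "Table 1 provides a complete list of the procedures at each study visit". In the text copy, the row "Urine pregnancy test (reproductive females" carries a mark under Visit 1 (baseline and randomization) and Visit 4 (final) and nothing under the two crossover visits.

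The visit narratives do not mention a pregnancy test at all. At Visit 1 they say "Baseline safety bloods (CBC & metabolic panel), a 12-lead ECG and a physical and neurological exam will be obtained", and at Visit 4 "We will obtain safety bloods, urinalysis, a 12-lead ECG and all patients will undergo a physical and neurological evaluation". Neither sentence names the test, although Table 1 marks it at both visits.

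Section 4.2 excludes pregnant and lactating women. Section 1.6.1 reports no controlled trials of carbidopa in pregnancy, and no teratogenic effect in mouse or rabbit at up to 120 mg/kg/day. Sections 4.1 and 4.2 state no contraception rule. The consent pages are not part of the text reviewed and may contain one.

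**The concern.** This is a three-period crossover. A new batch of study drug is started after Visit 2 and again after Visit 3. If the test is done only at Visits 1 and 4, a pregnancy that a urine test would have shown at Visit 2 could be followed by one or two further active periods, unless it came to light some other way. The Visit 4 test comes at the end of the last treatment period, so it can reveal exposure but cannot prevent it.

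The stake is participant safety. The point does not touch the endpoints, the power calculation, the error rate or the primary analysis.

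**Working it through.** **1. Can the blanks be trusted?** Table 1 has 23 rows. Leaving out consent, eligibility and the pregnancy test leaves 20 for comparison:

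- 15 rows show a mark at both Visit 2 and Visit 3.
- 5 rows show one of the two. Four are blank at Visit 2: 24-hour urine catecholamines, supine/seated/standing BP, beat-to-beat recording at rest, and Stroop. One, "Symptom/AE diary collection", is blank at Visit 3.
- No row shows neither.

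The text calls for the procedures in those five blank cells. The Fig. 6 caption (section 1.5) and the Visit 2 narrative place the first four at Visit 2. For the diary, the telemedicine text says "Symptoms diaries will be collected" and later "This protocol will be repeated for each telemedicine visit". So a blank cell in this copy does not show that a procedure was left out. A row missing both interim marks would be unlike any other, which makes genuine blanks the more probable reading but does not settle it.

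**2. The plan's own calendar.** The appendix sample instructions give a visit on Apr 2, new drug on Apr 6 and the next visit on May 4.

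- Visit to next start: Apr 2 to Apr 6 = 4 days (2 taper + 2 washout, as in the section 1.4 overview).
- Start to next visit: Apr 6 to May 4 = 28 days.
- Visit to visit: 4 + 28 = 32 days.

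**3. Period starts**, taking Visit 1 and the first dose as day 0 (an assumption):

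- Visit 2 = 28; period 2 starts 28 + 4 = **32**.
- Visit 3 = 32 + 28 = 60; period 3 starts 60 + 4 = **64**.
- Visit 4 = 64 + 28 = 92, so the two marked tests are 92 days apart.

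**4. Other readings.**

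- The Fig. 7 caption (section 3.1) spaces visits 28 days apart. Then Visit 3 = 56, period 3 starts 56 + 4 = 60, and Visit 4 = 3 × 28 = 84. Period 2 still starts at 32.
- The same caption allows 14 days around scheduled office visits. On a fixed schedule, period 2 starts at 32 ± 14 = 18 to 46 and period 3 at 64 ± 14 = 50 to 78. If two shifts accumulate, period 3 starts at 64 ± 28 = 36 to 92.
- Against the stated 14 weeks (98 days), the 32-day spacing ends at 92 days (13.1 weeks), or 99 with the follow-up call. The 28-day spacing ends at 84 days (12 weeks), or 91 with the call. The first is closer on either count, though the caption places the call after study completion, so the check is not exact.

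**5. Active treatment after Visit 2** (taper excluded):

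| Sequence | Period 2 | Period 3 | Active days |
|---|---|---|---|
| High/low/placebo | low | placebo | 28 |
| Low/placebo/high | placebo | high | 28 |
| Placebo/high/low | high | low | 28 + 28 = 56 |

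**6. With tests added at Visits 2 and 3.** Intervals between tests are 28, 32 and 32 days, so the longest falls from 92 to 32. The last test precedes the period start by 32 − 28 = 4 and 64 − 60 = 4 days, if it is done on the visit day.

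**The case against.** The strongest objection is that no rule is broken. Section 4.2 is an entry criterion, the test is marked at entry, and nothing in the documents requires a repeat. That stands. A reader might infer that the schedule contradicts the pregnancy exclusion, or that it exposes women to a known hazard. The documents support neither: the exclusion governs enrolment, and section 1.6.1 reports an absence of controlled data in pregnancy, not harm.

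Second, the table is damaged, and four of the five blank cells lie in consecutive rows of one column. Losses therefore cluster, and the 15/5/0 count cannot be turned into a probability. That also stands, and it is why the point is conditional. Section 8.6.1 adds almost nothing: "Safety data will be collected at each study visit (12 lead ECG, urinalysis, CBC, metabolic panel, vitals, neurological & physical examinations" omits a pregnancy test, but it also omits adverse event questioning, which Table 1 marks at every visit, so that list is not exhaustive. The narratives are equally uninformative, being silent even where the test is marked.

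Third, pregnancy might be noticed through examination, adverse event questioning, weekly calls or the diary, and the removed pages may carry instructions. This narrows the gap without closing it. Nausea is common in this disease and is a routine diary item, so it would be a poor signal of pregnancy (an inference, not a statement in the protocol).

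Fourth, a reader might take 32 and 64 days as two fixed starts of active drug. They are nominal, and only placebo/high/low has active drug in both later periods.

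**Conclusion.** The point holds as a minor, conditional safety improvement. If the original table has the ticks, it falls away. If the blanks are genuine, the last test precedes periods 2 and 3 by nominally 32 and 64 days, and every sequence still has 28 or 56 active days after Visit 2.

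The figures rest on a first dose on the day of Visit 1 and on the appendix calendar; the 28-day reading changes only the second figure, to 60, and the visit window widens both. The documents give neither the number of reproductive females nor a pregnancy rate, so no number of affected participants can be estimated.

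**What to change.** Check the row against the original Table 1. If Visits 2 and 3 are blank there:

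- Mark the urine pregnancy test at both visits for reproductive females. Run it on the urine already collected for urinalysis, or as a local or home test for televisits.
- Require a negative result before the first dose of the next period. In the office, read it before handing over the next bottle. For televisits, tell the participant not to start until released.
- If positive, do not start the next period and inform the investigator, who can already remove a patient for safety (section 4.3). State who else is told when the participant is a minor or a guardian has consented.

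The cost is two strips per eligible participant and no extra visit. As an illustration only, if 25% to 50% of 30 to 36 participants were eligible, that is 0.25 × 30 = 7.5 (about 8) to 0.50 × 36 = 18 people, or 16 to 36 strips.

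The real burden is the televisit hold-and-release step within the 4 days of taper and washout, with a possible short delay. The existing start-day call cannot serve as the release unless it is moved: on the sample calendar it comes at 10:00 AM, after the 8:00 AM first dose. Where televisit urine is collected before the call, the gap will be somewhat longer than 4 days. A very early conception may still be missed until the next test.
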